6.3 Comparator strategy

Many standardized questions were used in the development of the health questionnaire. Sources of these questions included the CCHS, the HRQOL-4, and work done by Smith-Sivertsen et al. (2000). The benefit of using standardized tests is that there exists data that has been previously collected for which comparisons can be made.

6.3.1 CCHS Data

The Canadian Community Health Survey is an instrument used by Statistics Canada to collect health data at both the health region and province/territory levels. The survey targets persons 12 years or older, living in private dwellings in 10 provinces and 3 territories. Exclusions include persons in institutions, persons living on Indian Reserves or Crown lands, full-time members of the Canadian Armed Forces and residents of remote regions. The CCHS takes a representative sample of approximately 98% of the Canadian population aged 12 and older (over 130,000 nationwide, approximately 30,000 in the province of Ontario). The data is currently available for the content of the September 2000 version, and comparisons will be made to that data for Ontario.

6.3.2 HRQOL-4 Literature

The HRQOL-4 was developed by the Centers for Disease Control and Prevention (CDC). In addition to the reference data available on U.S. citizens, a recent study performed in

Ontario provides data on 1, 042 individuals that was collected in a community-based study (Ôunpuu et al., 2000).

6.3.3 Smith-Sivertsen et al. (2000) Work

Smith-Sivertsen et al. (2000) published work in which they assessed the symptoms reported by 3,729 individuals, 18-69 years of age, who were exposed to occupational pollutants.

6.3.4 Reference Values and Population Normal Data

There are very few questions in the health questionnaire that do not come from standardized questionnaires. In these instances, prevalence data from published literature will be used to assess the data collected in this study.

With respect to laboratory and clinical data, standard reference ranges supplied by the laboratory (see Appendices 11.4 and 11.5) and standard clinical practice guidelines will be used to describe these outcomes.

6.4 Statistical Analysis

The frequency distributions of variables collected within the health questionnaire and medical tests will be tabulated. The number of missing responses for each variable will be presented, and where possible, these missing values will be treated as a separate category. Particular attention will be given to examining response rates for income levels, since this variable will be used as a proxy to socioeconomic status. If necessary, other factors, such as education, may need to be used instead.

Prevalence rates for health conditions will be calculated by age-group for males and females. Statistically significant differences across strata will be evaluated by using the Chi-Square and likelihood ratio tests for categorical data, and the Student's t-test for continuous data. Multivariate analysis of variance will be used to adjust comparisons for the influence of potential confounding variables. Comparisons will need to take into account possible differences in the age and sex structure of the populations being compared. Of particular interest will be the comparison of Area 3 (otherwise known as the Rodney Street area) to the rest of Port Colborne. Comparisons will also be made to reference data for Ontario or other normative data.

To evaluate the potential influence for response bias, where possible, socio-economic characteristics will be compared between non-respondents and participants. These variables will include: age, sex, family size, income level, and neighborhood of residence. Statistical tests of significance will be performed to determine whether non-responders differed from those who participated in the survey. Response bias will also be examined by comparing survey results obtained from the 1996 Canadian census data.

The prevalence of selected health characteristics will be compared to responses obtained from participants of the 2000 CCHS. In order to control for differences in the underlying populations, direct standardization will adjust for the age and gender make-up of the populations being compared. The ratio of these standardized rates will be calculated, and

95% confidence intervals of this ratio will be used to assess statistically significant differences.

Univariate statistics will be calculated for each chemical, as determined by laboratory analysis, to summarize the levels of the CoCs. These statistics will include: the mean, median, range, standard deviation and upper and lower percentiles. Tests for normality will be conducted to determine whether transformations of the CoCs values may be necessary for some multivariate modeling procedures. Variations in exposure levels within Port Colborne will be explored by calculating these summary statistics separately across different areas within the city. Differences across regions will be evaluated using multivariate regression analyses. Lognormal transformations are frequently applied to exposure distributions that are skewed. For CoCs with a large number of non-detectable levels, logistic regression analysis will be used to model those with exposure above the median CoCs level, relative to those with exposure below the median value.

Logistic regression methods will be used to evaluate the relationship between exposure to CoCs and selected health conditions. Because exposure to CoCs has been measured using two instruments (i.e., biological specimens and health questionnaire items), logistic regression analysis will be performed using these two series of independent variables. Pearson correlations coefficients and categorical analyses will be used to examine the concordance between the exposure measures from the laboratory and the summary measure estimated from the questionnaire.

The logistic regression model will provide a parameter estimate that can be readily transformed into an odds ratio. This odds ratio provides a measure of risk that can be used to determine whether those with high levels of exposure to CoCs are more likely to have a specified health condition. Survey participants will be categorized into tertiles based on their clinical exposure measurements and into binary groups based on the answers they give to the exposure question in the health questionnaire. Risk estimates will be calculated by comparing the prevalence of disease among those in the highest tertile of exposure to those in the lowest and for those indicating exposure in their answers to the questionnaire versus no exposure. The 95% confidence intervals for these odds ratios will also be calculated. This confidence interval can be used to determine whether or not the association may be due to chance. These estimates of risk will be adjusted for the potential confounding influence of other relevant variables, such as age, sex, smoking habits, alcohol use, and indicators of socio-economic status. All statistical analyses will be conducted by using SAS. The fit of the model will be assessed by using the Hosmer-Lemeshow goodness of fit statistic.

Multivariate analysis of variance will be used to compare laboratory measures of CoCs taken in Port Colborne residents to a normative sample. These multivariate models will be adjusted by age and sex of the subjects. Differences between the two populations will be evaluated by using the F-test statistics generated from the ANOVA model. Where necessary, measured levels of CoCs will be transformed in order to ensure that assumptions of normality are satisfied. If this assumption cannot be met through a

transformation, than non-parametric methods (e.g., Wilcoxon Rank Sum test) will be considered.

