4.1.3 Randomization of Subjects

In general, a sample consists of the sampling units chosen from the population eligible to be included. The sampling unit is the unit around which the sampling procedure is planned, and in this study, the unit will be defined as the individual. The sampling frame is the list of all the sampling units in the population. A list of all residential telephone numbers that are publicly listed will be used in this study. This phone list is sorted by area code, and includes phone, name and address information for roughly 6,700 households. Based on the most recent aggregate data from Canada Post, this represents 85.3% (6,700/7,856) of households in Port Colborne. The sampling method is the way in which the sampling units are chosen from the sampling frame. As described above, the sampling method for this study will be a stratified random sampling approach. For stratification, the sampling frame will be divided into five geographic areas categorized by level of exposure to the CoCs. By assigning a random number to each telephone listing within each stratum and then sorting these listings by this random number, the sorted listings can be used to randomly select households for inclusion in the study. Within each household, participants will be randomly selected taking into account the number of residents. Specifically, for a household with r residents, the k th oldest resident will be chosen where k is a random number between 1 and r . The telephone interviewers will be supplied with tables of random numbers for households ranging from sizes of 2 to 10 to select a value for k .

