6.1.1 Power calculations for the health questionnaire

Power was calculated based on the primary objective of the study which is to characterize the current health of residents in Port Colborne using a comprehensive health assessment questionnaire and medical testing. As mentioned previously, a stratified sampling strategy will be applied to recruit individuals from five geographical areas. The sample size of the Health questionnaire and medical tests was calculated by determining the number of individuals needed to measure the prevalence of selected health conditions with sufficient precision both within the Rodney Street Area, and the remainder of Port Colborne. Specifically, the sample size of 1,000 was selected to ensure that a 5% prevalence of asthma could be measured within an accuracy of 2% 16 times out of 20, and that the prevalence of nickel sensitivity estimated at 9.5% among women could be measured within 7% and 13% 16 times out of 20 (see Table 1 below).

Table 1: Sample Size Needed to Compare Disease Prevalence Rates (Proportions)

Health Condition	Anticipated Prevalence	Prevalence Range Permitted**	Subjects needed in Area 3	Subjects needed in remainder of Port Colborne	Minimally detectable Odds Ratio*
Asthma	5%	4-6%	418	777	2.0
Asthma	5%	3-7%	160	193	3.2
Asthma	5%	4.5%-5.5%	699	2662	1.7
Cancer	0.5%	0.4-0.6%	811	5630	3.4
Nickel Sensitivity (females)	9.5%	8%-11%	370	607	1.8
Nickel Sensitivity (females)	9.5%	7%-13%	181	223	2.4

* Comparison of prevalence of disease between Area 3 and the rest of Port Colborne

**with Power of 80% and an alpha error of 5%

Assuming that there is a response rate of 65%, and that 50% of residents in the region are female, there will be 234 female participants in the Rodney Street area and a remaining 251 female subjects in the rest of Port Colborne. This will enable nickel sensitivity to be measured with sufficient precision as outlined in the table above. Moreover, when supplemented with data obtained from males, there will be sufficient precision to measure the prevalence of asthma within an accuracy of 2% in both sexes (see Table 1). It is important to note that due to the rarity of cancer, the health questionnaire is unable to measure the prevalence of cancer in Port Colborne with sufficient precision. The evaluation of this health outcome will be addressed in a subsequent research protocol.

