The estimated number of dwellings and individuals that make up the target population are listed in Table 1. This list is considered approximate as it is based on Canadian census data obtained in 1996.

Table 2: Estimated Number of Households and Individuals 12 years of Age and Older* within Each Sampling Region for the health questionnaire.

Region (EA's)	Number of private dwellings	Estimated population 12 years of age and older
1- West of the Welland Canal, south of Clarence and Augustine Road (151-156)	1,945	4,055
2- West of the Welland Canal, north of Clarence (116-120)	2,260	4,798
3- East of the Canal, south of Durham (includes Durham) and is bounded by Davis and Lake (110)	365	719
4 - East of the Canal, north of Durham (excludes Durham) and is bounded by Snider Road (106,108)	775	2,346
5- Other areas of Port Colborne (101-105,107,109,112-113)	2,030	4,437
Total	7,375	16,355

* assumes that 85% of the Port Colborne community is 12 years of age and older (based on 1996 Census data from Statistics Canada).

It is very important to note that while there are sufficient numbers to measure the prevalence of the selected health conditions with the desired precision, there is limited power to make comparisons between rates in the Rodney Street area to the remainder of Port Colborne. Specifically, with 500 subjects recruited in both the Rodney Street area and other parts of Port Colborne, the study has the power to detect an odds ratio of 2.1 for the comparison of asthma rates between the two regions with a power of 80% and a type I error rate of 5%. The odds ratio of 2.1 corresponds to a greater than two-fold increased prevalence rate in area 3 relative to the rest of Port Colborne. Similarly, for a comparison of nickel sensitivity rates in females between the two regions, there is power to detect an odds ratio of 2.2.

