Comparison of the Mean Levels of Selected Biological Measures, by Sampling Areas,
CHAP Comprehensive Health Questionnaire, Fall 2002

	Area 3	Areas 1, 2, 4, 5	Total for Port Colborne	p-value [†]
	Mean (s.d)*	Mean (s.d)	Mean (s.d)*	
Haemoglobin				
White Blood Cell Count				
Red Blood Cell Count				
Haematocrit				
Mean Cell Volume of Red Cells				
Mean Hemoglobin Concentration of Red Cells				
Platelet Count				
Red Cell Distribution Width				
Mean Platelet Volume				
Differential Leukocyte Count				
Bilirubin				
Creatinine				
Plasma Cotinine				
Plasma Screen for Concentration of TSH				
Blood Urea Nitrogen				

[†] p-value is based on an ANOVA for comparing the means between Area 3, and Areas 1, 2, 4, and 5; after adjusting for difference in the age and sex distribution of the two populations.

* s.d. = standard deviation

Table 8.
Comparison of the Non-Specimen Tests Among Participants, by Sampling Areas,
CHAP Comprehensive Health Questionnaire, Fall 2002

	Area 3	Areas 1, 2, 4, 5	Total for Port Colborne	p-value [†]
	Mean (s.d) [*]	Mean (s.d)	Mean (s.d.)	
Calculated BMI				
Electrocardiogram	---	---	---	---
Blood Pressure				
Carbon Monoxide Breath Test				
Forced Expiratory Volume in 1 second				
Forced Vital Capacity				
Peak Expiratory Flow Rate				
Dermatology Patch: Nickel Sulfate				
Dermatology Patch: Cobalt Dichloride				

[†] p-value is based on an ANOVA for comparing the means between Area 3, and Areas 1, 2, 4, and 5; after adjusting for difference in the age and sex distribution of the two populations.

^{*} s.d. = standard deviation

Table 9.
Comparison of the Selected Measures of Chemicals Among Participants, by Sampling Areas, CHAP Comprehensive Health Questionnaire, Fall 2002

	Area 3	Areas 1, 2, 4, 5	Total for Port Colborne	p-value [†]
Chemical	Mean (s.d) [*]	Mean (s.d)	Mean (s.d)	
Nickel (Urine)				
Copper (Urine)				
Cobalt (Urine)				
Arsenic (Urine)				
Mercury (Urine)				
Lead (Blood)				

[†] p-value is based on an ANOVA for comparing the means between Area 3, and Areas 1, 2, 4, and 5; after adjusting for difference in the age and sex distribution of the two populations.

^{*} s.d. = standard deviation

Table 10.
Comparison of the Proportion of Tests Outside Normal Range for Selected Biological Measures,
by Sampling Areas,
CHAP Comprehensive Health Questionnaire, Fall 2002

	Area 3	Areas 1, 2, 4, 5	Total for Port Colborne	p-value [†]
Proportion Outside Normal Range				
Haemoglobin (normal range)				

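### The pooled-variance tests for Area 3 against the rest are nearly harmless at the stated group sizes, but would lose their 5% error rate at the smaller Area 3 sample that the household sampling rule allows, if the spreads differ

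*Protocol*

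**What the plan says.** For differences across strata, Protocol section 6.4 names Student's "t-test for continuous data. Multivariate analysis of variance will be used to adjust comparisons for the influence of potential confounding variables". It singles out one contrast: "Of particular interest will be the comparison of Area 3 (otherwise known as the Rodney Street area) to the rest of Port Colborne". In section 6.5.1 the footnotes to Tables 7, 8 and 9 (laboratory values, non-specimen tests, metals) say that the "p-value is based on an ANOVA for comparing the means between Area 3, and Areas 1, 2, 4, and 5", adjusted for age and sex. No unequal-variance version is mentioned.

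On group sizes, section 6.1.1 speaks of power "with 500 subjects recruited in both the Rodney Street area and other parts of Port Colborne" and, at 65% response, says "there will be 234 female participants in the Rodney Street area and a remaining 251 female subjects in the rest of Port Colborne". Table 2 of that section gives Area 3 as 365 private dwellings and 719 residents aged 12 or older.

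Section 4.1.3 samples from a telephone list, draws households at random within each stratum and then takes one resident per household. Of the list it says "this represents 85.3% (6,700/7,856) of households in Port Colborne".

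**The concern.** Student's t-test and ordinary ANOVA estimate one common variance. The result is sound if the two variances are equal, and nearly so if the two groups are of equal size. If both fail, the standard error is wrong. It is too small when the smaller group is the more variable, and too large when the larger group is.

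The stated plan has near-equal groups, but the sampling rule in section 4.1.3 does not appear able to deliver them. Equal spread is also not assured. Area 3 is oversampled because exposure may be higher there, section 6.4 anticipates skewed exposure distributions, and the comparison group merges four areas defined by differing exposure. At stake is the calibration of the p-values in Tables 7-9 for the contrast that the protocol cares about most.

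**Working it through.** **1. The plan's own group sizes.** From 719 residents, 65% response and 50% female (section 6.1.1): 719 × 0.65 × 0.50 = 233.7, which is the stated 234 women. Doubling the stated figures for both sexes gives 468 against 502. The plan's count therefore treats every Area 3 resident aged 12 or older as selectable.

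**2. Group sizes under section 4.1.3.** One resident per household, 365 dwellings in Area 3:
- upper limit, with full listing and full response: 365, leaving 635 of 1,000 elsewhere;
- 65% response: 365 × 0.65 = 237, leaving 763;
- 65% response and 85.3% of households listed: 365 × 0.853 × 0.65 = 202, leaving 798, or 502 if the rest is not topped up to reach 1,000.

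The 85.3% is a citywide figure. Applying it to Area 3 is an assumption.

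**3. Error rate of a nominal 5% pooled test.** Let n1, s1 be the size and SD in Area 3, n2, s2 those of the rest, with no true difference in means.
- Pooled variance: Sp² = [(n1 − 1)s1² + (n2 − 1)s2²] / (n1 + n2 − 2)
- Variance the test uses: Vp = Sp² × (1/n1 + 1/n2)
- True variance of the difference: Vt = s1²/n1 + s2²/n2
- Two-sided error in large samples: 2 × [1 − Φ(1.96 × √(Vp/Vt))]

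Example, 202 against 798 with s1 = 2, s2 = 1: Sp² = (201 × 4 + 797) / 998 = 1.604; Vp = 1.604 × (1/202 + 1/798) = 0.00995; Vt = 4/202 + 1/798 = 0.02106; Vp/Vt = 0.473; error = 17.8%.

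The protocol gives no SD for any measure, so the SD ratio (Area 3 / rest) is an assumed range.

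| Area 3 v rest | Ratio 0.67 | Ratio 1.5 | Ratio 2 |
|---|---|---|---|
| 500 v 500 (stated) | 5.0% | 5.0% | 5.0% |
| 468 v 502 (stated, both sexes) | 4.7% | 5.3% | 5.5% |
| 365 v 635 | 3.0% | 7.7% | 9.6% |
| 237 v 763 | 1.6% | 11.1% | 15.8% |
| 202 v 502 | 2.1% | 9.7% | 13.1% |
| 202 v 798 | 1.3% | 12.1% | 17.8% |

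At a ratio of 0.5, 468 against 502 gives 4.5%.

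**4. Check by simulation.** With normal data and 20,000 runs per setting, the pooled test at 200 against 800 gave 1.2%, 11.9% and 18.3% for ratios 0.67, 1.5 and 2. Welch's test gave 4.8-5.2% in every setting tried (500/500, 468/502, 234/251 and 200/800; ratios 0.5 to 2).

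**5. Cost in power.** With equal variances, 202 against 798 and a true difference of 0.22 SD, power is about 79% with either test.

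**The case against.** The strongest reply is that the protocol plans near-equal groups, where the error stays within about half a percentage point of 5%. That is correct. A reader might infer that the groups will certainly be very unequal and that the error will be 12-18%. The documents do not support that:
- The upper figures need a split near 1:4 together with an assumed SD ratio of 1.5-2 and the larger spread in Area 3. If the rest is the more variable, the test is conservative instead.
- The 202 borrows a citywide list coverage, and the 798 assumes that an Area 3 shortfall is refilled elsewhere. Section 4.1.1.2 provides replacement for drop-outs but does not say from which stratum.
- The one-per-household rule is itself not consistent throughout. The questionnaire header in Appendix 10.1 has all household members aged 12 or older answering. On that reading, with list coverage and 65% response, 719 × 0.853 × 0.65 = 399 against 601, and the error is 3.4%, 7.0% and 8.3% at ratios 0.67, 1.5 and 2.

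Two further objections have weight. Section 6.4 foresees transforming skewed metal levels, and a log scale often evens out spread that grows with the mean. But that provision, like the Wilcoxon fallback, is aimed at non-normality of metal levels. It does not address unequal spread, or the measures in Tables 7 and 8. Also, if higher exposure is what widens the spread of a metal in Area 3, its mean probably differs too, so a false-positive rate is not the whole matter. The standard error would be wrong all the same.

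Finally, the calculation is for an unadjusted two-group test. In the mock tables the t-test itself appears only under Table 3, while Tables 7-9 use adjusted ANOVA. The pooled-variance assumption is shared, but the percentages are a guide to the adjusted analysis and not exact values for it. The choice might be refined in a later analysis plan, but the protocol does name the tests.

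**Conclusion.** The point holds as a minor one. The named tests rely on a common variance, which is nearly harmless at the stated sizes (4.5-5.5% for SD ratios 0.5 to 2). At the sizes the household rule can deliver, and for an assumed SD ratio of 0.67 to 2, the true error of a nominal 5% test would be about 3.0-9.6% (365 v 635), 1.6-15.8% (237 v 763), 2.1-13.1% (202 v 502) or 1.3-17.8% (202 v 798).

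These ranges rest on assumed SD ratios, on one resident per dwelling, on 65% response and, for the 202, on the citywide list coverage. The protocol establishes neither that the spreads differ nor in which direction. What it does show is that its stated Area 3 sample of 468-500 cannot come from 365 dwellings at one resident each, so the near-equal split that makes pooling safe should not be relied on.

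**What to change.** In section 6.4, replace Student's t-test with Welch's unequal-variance t-test. In the footnotes to Tables 7-9, base the age- and sex-adjusted comparison on regression with heteroscedasticity-consistent standard errors, on whichever scale (raw or log) is analysed. This is a wording change and a standard option in SAS. It needs no further data, costs practically no power, and keeps the error near 5% whatever split is reached.

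Separately, reconcile the one-resident-per-household rule of section 4.1.3 and the questionnaire header in Appendix 10.1 with the Area 3 numbers in section 6.1.1. Changing the test does not resolve that conflict.
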